### 9.4.1.2. Supplementary Analyses

As a supplementary analysis, the percent change from baseline in serum 17-OHP at Week 4 will be analyzed using the same method as described in the primary analysis of this endpoint. Missing

data will also be imputed using the same methods as described in the primary analysis of this endpoint.

As a supplementary analysis, the change from baseline in serum 17-OHP at Week 4 will be analyzed using the average of all serial sampling 17-OHP values at Day 1 and Week 4. If all Day 1 17-OHP values are missing, then the screening 17-OHP value will be used instead. Note that subjects <6 years of age or <20 kg will have only a single serum 17-OHP value for both baseline and Week 4. This analysis will be performed using the same method as described in the primary analysis of this endpoint. Missing data will also be imputed using the same methods as described in the primary analysis of this endpoint.

As a supplementary analysis, the change from baseline to Week 4 in serum 17-OHP, derived as a multiple of the ULN (calculated as the observed value divided by the ULN value), will be analyzed using the same method as described in the primary analysis of this endpoint. Missing data will be imputed using the same methods as described in the primary analysis of this endpoint.

### 9.4.2. Glucocorticoid Daily Dose

The second key secondary endpoint is the percent change from baseline in glucocorticoid daily dose (in hydrocortisone dose equivalents adjusted for BSA [mg/m^2/day]) at Week 28, while Week 28 serum and rost endione is  $\leq 120\%$  of the baseline value or  $\leq ULN$ , according to sex and either age (for Tanner stage 1) or pubertal stage (for Tanner stages 2 to 5). Glucocorticoid daily dose will be calculated at baseline (as defined in Section 6.3.1) and at Week 28 using the doses reported on the glucocorticoid medications eCRF (see details in Section 6.7 regarding mapping of the glucocorticoid medication to Week 28). Glucocorticoids other than hydrocortisone (ie, methylprednisolone, prednisolone, and prednisone) will be converted to hydrocortisone equivalents using an equivalency ratio as described in Section 6.6. BSA will be calculated using the DuBois formula (Section 7.3). The calculation of glucocorticoid dose in hydrocortisone equivalents adjusted for BSA at Day 1 and Week 28 will be based on height and weight measurements at Day 1 and Week 28, respectively. If glucocorticoid dosing alternates over the course of two consecutive days, then the average of the glucocorticoid dose on those days will be used to calculate the glucocorticoid daily dose. If glucocorticoid dosing alternates between weekdays and weekends (or another weekly regimen that varies by day of the week), then the average daily dose will be calculated as the sum of the glucocorticoid doses over the 7-day period divided by 7.

The serum androstenedione values at baseline and Week 28 to be used in the assessment of androstenedione "control" is defined in Section 6.3.5.

Subjects who have a decrease in glucocorticoid daily dose at Week 28 and who are not able to maintain their serum androstenedione at Week 28 at  $\leq 120\%$  of their baseline value or  $\leq ULN$  for sex and either age (for Tanner stage 1) or pubertal stage (for Tanner stages 2 to 5) will be considered to have a 0 percent change from baseline in the glucocorticoid daily dose at Week 28. Subjects with an increase in glucocorticoid daily dose at Week 28 will have their observed glucocorticoid daily dose value used regardless of androstenedione control. Subjects who are missing glucocorticoid dose at Week 28 and serum androstenedione at all timepoints at the Week 28 visit will have their data imputed through the multiple imputation procedure described in Section 17.2.

The primary analysis of this endpoint will be performed using an ANCOVA model, as described in Section 9.2.1. The model will include treatment group, baseline glucocorticoid daily dose  $(mg/m^2/day)$ , and stratification factors used in the randomization.

Descriptive statistics will be presented by treatment group for the glucocorticoid total daily dose  $(mg/m^2/day)$  observed, change from baseline, and percent change from baseline values at baseline (observed data) and each postbaseline visit. Mean (±SEM) values of the glucocorticoid total daily dose at each visit will be summarized in line graphs by treatment group. Similar graphs will be presented for the change from baseline and percent change from baseline. These summaries will be presented for both the glucocorticoid total daily doses *without* the derivation of 0 for loss of androstenedione control as well as the glucocorticoid total daily doses *with* the derivation of 0 for loss of androstenedione control (for change from baseline and percent change from baseline summaries only).

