## 9.3.2. Glucocorticoid Dosing and Dose Reduction

Each subject will record their daily glucocorticoid regimen in the electronic diary (eDiary) beginning at the screening visit until Week 52 (or Week 56 if subject does not enter OLE), including specific type of glucocorticoid and all doses taken each day for their usual regimen as well as any additional or stress dosing. The usual daily regimen will be converted to hydrocortisone dose equivalents (mg/m²/day; with a hydrocortisone equivalency ratio of 4 for methylprednisolone, prednisolone, and prednisone) adjusted for BSA for the purpose of analysis.

Guidelines for reducing or optimizing glucocorticoid dose should be followed in order to evaluate the efficacy of the study drug, except in the event that a subject requires stress dosing (Section 9.7.2). If a subject's glucocorticoid regimen is adjusted due to stress dosing, the subject should resume their glucocorticoid dosing regimen for at least 3 days before their next scheduled lab test if the duration of stress dosing is 3 days or less, and for at least 7 days before their next

scheduled lab test if the duration of stress dosing is  $\geq 4$  days (of note, this 3- or 7-day window supersedes all other visit windows).

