## 6.3.5. Baseline Definition of Serum Androstenedione "Control" for Second Key Secondary Endpoint

The second key secondary endpoint is the percent change from baseline in glucocorticoid daily dose (in hydrocortisone dose equivalents adjusted for BSA [mg/m^2/day]) at Week 28, while androstenedione is in "control". Androstenedione is considered in "control" if the Week 28 serum androstenedione is  $\leq 120\%$  of the baseline value or  $\leq ULN$ , according to sex and either age (for Tanner stage 1) or pubertal stage (for Tanner stages 2 to 5). For all subjects, baseline serum androstenedione used to define "control" will be defined as the average of all pre-morning glucocorticoid serum androstenedione values on Day 1. Subjects who are <6 years of age or <20 kg will have only a single pre-morning glucocorticoid serum androstenedione value for baseline and Week 28. If values on Day 1 are missing, the last pre-morning glucocorticoid serum androstenedione value prior to Day 1 will serve as the baseline. The pre-morning glucocorticoid

dose androstenedione value at Week 28 will be used for the comparison to the baseline androstenedione in assessing control (as defined above). If the pre-morning glucocorticoid dose androstenedione value at Week 28 is not available, the post-morning glucocorticoid dose value will be used. The missing data handling approach is described in Section 9.4.2.

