The second key secondary endpoint of percent change from baseline in glucocorticoid daily dose at Week 28 is based on the glucocorticoid concomitant medications eCRF. The method of collecting concomitant medication data involves entering a start date and stop date for each medication, unless it is ongoing, in which case the "Ongoing?" field is marked as "yes." This differs from assessments that are collected discretely at visits. Additionally, the androstenedione values collected at the Week 28 visit are a critical component to the assessment of this endpoint as subjects who do not maintain androstenedione control and have a decrease from baseline in glucocorticoid total daily dose will have their percent change from baseline value in glucocorticoid total daily dose set to 0. For the purposes of determining the glucocorticoid total daily dose from the eCRF at Week 28, the Week 28 visit date at which the androstenedione values were collected (based on the analysis visit mapping described below) will be used to determine the glucocorticoid dose (as of the same date) to be used for the second key secondary endpoint. If a subject has a Week 28 visit performed based on the analysis visit window but androstenedione was not collected at this visit (ie, missed hormone labs), then the analysis visit date from the collection of the safety labs will be used instead for determining the Week 28 glucocorticoid total daily dose. If both hormone and safety labs were missed at the visit, then the vital signs assessment and its respective Week 28 analysis visit date will be used for determining the glucocorticoid total daily dose. The same methodology described above will be used to determine the glucocorticoid total daily dose from the eCRF at each of the other intermediate visits.

Table 4 includes the analysis visit windows for all assessments, with the exception of those assessments that have a broader window due to more infrequent assessments (ie, every 6-7 months). These more-infrequent assessments include measurements of bone age (via x-ray) and TARTs (via testicular ultrasound). These assessments will use the analysis visit windows defined in Table 6. Table 5 includes the analysis visit windows for subjects who discontinue from study drug prior to OL period or OLE and therefore do not have a first dose date in the OL period or OLE.

Scheduled Visit	Target Study Day	Analysis Window (Study Day Range)
Week 4	28	2 to 43
Week 8	56	44 to 70
Week 12	84	71 to 98

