### 9.3. Analysis of the Primary Efficacy Endpoint

#### 9.3.1. Primary Estimand

#### The Primary Estimand is defined by the following:

Population: Pediatric subjects in the FAS with classic CAH due to 21-hydroxylase deficiency on a stable, supraphysiologic glucocorticoid dose regimen (>  $12 \text{ mg/m}^2/\text{day}$ ) at study entry and have an androstenedione level (prior to the morning glucocorticoid dose) greater than the midpoint of the reference range. Subjects must have met the other inclusion and exclusion criteria defined in the protocol.

Variable (or endpoint) to be obtained for each subject: change from baseline in serum androstenedione at Week 4

Intercurrent events will be handled using the following strategy:

- 1) If a subject discontinues study drug but stays on study through Week 4 and has serum androstenedione measured at Week 4, the subject's observed serum androstenedione at Week 4 will be used in the analysis.
- If a subject is on study drug through Week 4 but is missing Week 4 serum androstenedione, the subject's endpoint will be multiply imputed from subjects within the same treatment group with non-missing data at Week 4 (Week 4 Completers) (Section 17.1).
- 3) If a subject in the crinecerfont treatment group discontinues study drug prior to Week 4 and is missing serum androstenedione at Week 4, the subject's endpoint will be multiply imputed using data from Retrieved Dropouts (Section 17.1). If there is an insufficient number of Retrieved Dropouts, the subject's endpoint will be imputed using observed data from subjects in the placebo treatment group (Section 17.1). For subjects in the placebo treatment group drug (prior to Week 4) and are missing serum androstenedione at Week 4, missing data will be imputed using non-missing data from subjects in the placebo treatment group (Section 17.1).
- 4) If a subject's Week 4 androstenedione value is obtained within a timeframe that could be confounded by stress dosing with glucocorticoids, the subject's androstenedione value

will be imputed using non-missing data from subjects in the placebo treatment group (Section 17.1).

Population-level summary: The least-squares mean treatment difference for this endpoint will be estimated using an ANCOVA model, as described in Section 9.2.1. Missing data will be imputed using the multiple imputation procedure defined in Section 17.1.

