### 14. DEVIATIONS FROM PROTOCOL PLANNED ANALYSIS

This section will document any deviations from the protocol planned analysis along with any assessments that were performed on study (and reviewed by the study site) but will not be summarized.

The following assessments were performed on study but will not be summarized:

- Physical examination results (excluding height, weight, and Tanner staging)
- CYP21A2 genotyping
- Pregnancy test
- Urine drug screen
- Urinalysis
- Glucocorticoid daily dose from eDiary

The following list includes all deviations from the protocol planned analysis:

- The Safety Analysis Set definition in the protocol specified that the subject must have postbaseline safety data during the double-blind placebo-controlled period. This part of the definition was removed from the SAP due to the potential issue of having a subject dosed with study drug and then becoming lost to follow-up.
- The Safety Analysis Set was split up into the DB Period Safety Analysis Set and the OL Period Safety Analysis Set.

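### The Week 28 glucocorticoid endpoint has no rule for an androstenedione value distorted by stress dosing, although the primary endpoint has one, and the plan does not say whether stress doses count in the Week 28 dose

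*SAP*

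**What the plan says.** **Control and credit.** SAP 9.4.2 looks at children whose dose has fallen and "who are not able to maintain their serum androstenedione at Week 28" at or below 120% of baseline or the upper limit of normal. They "will be considered to have a 0 percent change from baseline in the glucocorticoid daily dose at Week 28". Any other decrease is credited as observed, and any increase is used whatever the A4 (androstenedione). Under SAP 6.3.5, the pre-morning "dose androstenedione value at Week 28 will be used for the comparison to the baseline androstenedione in assessing control"; if it is unavailable, the post-dose value is used.

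**Dose.** SAP 9.4.2 calculates the daily dose "using the doses reported on the glucocorticoid medications eCRF". Under SAP 6.7, the date of the A4 sample "will be used to determine the glucocorticoid dose (as of the same date) to be used for the second key secondary endpoint". Protocol 9.3.2 has the eDiary capture all doses, including stress doses, but converts the usual daily regimen for analysis. SAP 14 lists "Glucocorticoid daily dose from eDiary" among the data that will not be summarized.

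**Stress dosing.** SAP 9.3.1, item 4, covers the case where the Week 4 "androstenedione value is obtained within a timeframe that could be confounded by stress dosing with glucocorticoids"; that value is imputed from placebo data. Protocol 9.3.2 also asks that the regimen be resumed "at least 3 days before their next scheduled lab test if the duration of stress dosing is 3 days or less", or for at least 7 days after a longer course. This takes precedence over the visit windows.

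**The concern.** At Week 28, A4 is the gate that decides whether a dose reduction counts. Extra glucocorticoid shortly before the draw can lower A4 (Protocol 5.1 describes glucocorticoid as suppressing ACTH and androgen production). A child whose A4 would be out of control on the reduced dose can then pass the gate and keep the credit. The sponsor saw this problem at Week 4 and wrote a rule for it, but wrote none for Week 28.

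The endpoint is third in the alpha-controlled sequence (SAP 9.1). SAP 9.5.1 uses the same conventions, so the responder endpoint is exposed too. The dose side is also unsettled: the SAP does not say whether a temporary stress dose active on the sampling date is the Week 28 dose.

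**Working it through.** **1. The plan's own figures.** None is given for this point. SAP 3.3 gives 54 crinecerfont and 27 placebo subjects, with power for the primary endpoint above 90% at effect size 0.83 and above 80% at 0.70. A noncentral t with 79 degrees of freedom gives 93.6% and 83.5%, so these reproduce. Only the arm sizes matter here.

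**2. The two visits compared.**
- Scheduling rule of 3 or 7 days after stress dosing: applies at both visits.
- Analysis rule for a draw taken too early: replaced at Week 4 (9.3.1, item 4); none at Week 28.
- Imputation: 17.2 acts only when the Week 28 dose or A4 is missing. A distorted value that is present stays in.

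**3. Other analyses of the endpoint (SAP 9.4.2.1 and 9.4.2.2).**
- Complete-case: keeps the value.
- Tipping point: shifts imputed doses only.
- 150% and 180% limits: loosen the gate.
- Latest or highest controlled dose: used only when control fails at Week 28, so false control bypasses it.
- No zeroing for lost control: unaffected by misclassified observed control, but it answers a different question and does not correct the primary analysis.

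**4. Size of a misclassification.** If k children in an arm of n move from 0% to a credited cut of R%, the raw arm mean moves by k × R / n. R = 25 is an assumption.
- One crinecerfont child: 25/54 = 0.46 points, in favour of crinecerfont.
- One placebo child: 25/27 = 0.93 points, against crinecerfont.
- Two crinecerfont and one placebo: −2 × 25/54 + 25/27 = 0.
- For R = 20 to 40: 0.37 to 0.74 points on crinecerfont and 0.74 to 1.48 on placebo.

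**5. Responder endpoint.** Response needs a dose of at most 11 mg/m²/day. A 25% cut reaches that only from a baseline of at most 11/0.75 = 14.67. Entry requires more than 12, with no upper limit (Protocol 8.1, criterion 4). A child who meets the limit moves the rate by 1/54 = 1.9 points on crinecerfont or 1/27 = 3.7 on placebo; a child who does not leaves it unchanged.

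**6. The dose ambiguity.**
- *Stress doses excluded* (the reading in Protocol 9.3.2): the suppressed A4 is paired with the lower usual dose, as in step 4.
- *Stress doses on the sampling date included* (a possible reading of SAP 6.7): Protocol Appendix A describes doubling or tripling hydrocortisone in illness. For a child on hydrocortisone alone after a 25% cut, 0.75 × 2 = 1.50 reads as +50% and 0.75 × 3 = 2.25 as +125%. Against −25%, these are errors of 75 and 150 points, or 1.4 and 2.8 points on the crinecerfont mean (n = 54) and 2.8 and 5.6 on placebo (n = 27).
- A course that ended before the draw is not counted on either reading, because only the dose on the sampling date is taken.

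**7. Frequency.** The documents give no stress-dosing rate. Assume 0.5 to 4 episodes per subject-year and a vulnerable window of 6 to 12 days. If no visit were moved, 81 × (1 − exp(−rate × window/365)) gives 0.7 to 10 draws of 81 inside the window. Misclassified children would be fewer: the draw must not have been moved, the dose must be reduced, and A4 must otherwise exceed both limits.

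**The case against.** The strongest reply is that conduct already guards against this. The 3- or 7-day rule overrides the visit windows, so an affected draw should be moved. SAP Table 4 runs Week 28 from Day 169 to the first open-label dose, so a moved draw still maps to Week 28. Deviations likely to affect a key secondary endpoint are reviewed before unblinding (SAP 7.2). All this stands as a reason to expect few cases. But the scheduling rule is worded as a recommendation, it does not say how to analyse a draw taken too early, and it applied equally at Week 4, where the sponsor still added an analysis rule.

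Three stronger readings are tempting, and the documents do not support them.
- *The gap favours crinecerfont.* False control can be credited in either arm, one placebo child moves its mean twice as far, and equal proportions cancel.
- *The plan definitely leaves stress doses uncounted, or definitely scores an ill child as a dose increase.* Protocol 9.3.2 points to the usual regimen; SAP 6.7 is silent. Neither outcome is a stated SAP rule.
- *Dropping the eDiary summary hides the affected draws.* SAP 14 says only that the eDiary dose is not summarized. Stress dosing is also documented on the eCRF (Protocol 9.7.2) and tabulated as a safety outcome (SAP 11.2.4), so the draws can be found.

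**Conclusion.** The gap holds. Followed exactly, the SAP accepts a Week 28 A4 suppressed by stress dosing as control and credits the dose reduction, in a confirmatory endpoint and in the responder endpoint that shares its rules. None of the planned sensitivity or supplementary analyses corrects this. SAP 6.7 and Protocol 9.3.2 also need to be reconciled on what the Week 28 dose is.

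The size is modest per child: 0.46 points on crinecerfont or 0.93 on placebo for an assumed 25% cut, with opposite effects on the treatment difference. These are raw-mean shifts; the ANCOVA estimate would differ somewhat. The responder rate moves only if the reduced dose is at most 11 mg/m²/day. How many children are affected, and the net direction, cannot be determined from the documents. The case for a change rests on the inconsistency with the sponsor's own Week 4 rule and on the low cost, and does not require a demonstrated bias.

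**What to change.** Before unblinding, amend SAP 6.3.5, 6.7, 9.4.2 and 17.2, with 9.5.1 following.

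1. Flag, from the eCRF or eDiary, any Week 28 A4 drawn within the protocol's own 3- or 7-day interval after stress dosing.
2. For a flagged draw, use an unconfounded pre-dose draw in the Week 28 analysis window if there is one, even if it is not the draw nearest Day 196. Only one pre-dose sample is scheduled (Protocol 9.8.2.7), so this will be uncommon.
3. Otherwise treat A4 as missing, without falling back on the same-day post-dose value, and impute it from placebo subjects as in 9.3.1, item 4. The current 17.2 rule for on-drug subjects draws on completers in the same arm; if most crinecerfont completers are controlled, it would often restore the credit.
4. State that the Week 28 analysis dose is the usual regimen without temporary stress doses, in line with Protocol 9.3.2.
5. Add a sensitivity analysis scoring flagged children with a dose decrease as 0% change and as non-responders. This matters because the A4 model in 17.2 uses baseline A4, age and sex but not the Week 28 dose, so placebo imputation is not guaranteed to be conservative.

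The cost is SAP wording, one data flag from records already collected, and a few more imputed values. No clinical procedure changes.

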#### 9.4.2.1. Sensitivity Analyses

The assumptions relative to the ANCOVA model (eg, linearity, normality) for the second key secondary endpoint will be checked and any violations of these assumptions will be handled through non-parametric statistical methods.

A tipping point sensitivity analysis will be performed to assess the robustness of the missingness assumptions. This sensitivity analysis is based on "delta adjustments" which is a commonly used approach to assess the impact of missing data in clinical trials (O'Kelly and Ratitch, 2014). The imputed Week 28 serum glucocorticoid daily dose values (from the MI procedure described in Section 17.2) for subjects in both the crinecerfont treatment group and the placebo treatment group will be delta-adjusted (with a range of plausible penalties for each treatment group) until the treatment difference at Week 28 is no longer statistically significant. The implementation procedure for the tipping point analysis is described in Appendix 17.5. The combinations of delta adjustments that tip the result from statistically significant to insignificant, along with the corresponding insignificant p-values, will be presented in a table and may be presented in a figure.

A complete-case sensitivity analysis will also be performed to test the robustness of the multiple imputation procedure. The ANCOVA analysis for the first key secondary endpoint will be repeated using only subjects with observed data at Week 28. Subjects who are missing any component of the Week 28 second key secondary endpoint will be excluded from the analysis.

Descriptive statistics and LS means for the complete-case sensitivity analyses will be presented by treatment group along with the LS-mean treatment difference, 95% confidence intervals, and nominal p-values.

